			9.5. Subject Status and Classification	Eligibility violation is considered a study deviation; safety check window is from 30 to 60 days after the attempted implant.	Clarifications.

Form/Template 92120219_Rev/Ver D
LUX-Dx PERFORM Protocol, 92557593, Rev/Ver C
Page 4 of 66

Revision Version	Protocol Date	Template number and version	Protocol Section Modified	Summary of Changes	Justification for Modification
			10.1. Data Collection	Visit activities and consolidated in the Data Collection Schedule table; virtual health visit option is added.	Modifications and providing subject with additional visit option (virtual health visit).
			10.4. Enrollment Visit	Clarify "Reason for Monitoring" determination.	Clarifications.
			10.5. ICM Implant Procedure	Adding implanter authorization requirement, R-wave amplitude collection, and evidence of device registration.	Addition of requirement and clarifications.
			10.6. ICM Reprogramming	Remove remote reprogramming required for the first 25-30 subjects, add cap of only requiring the first 5 reprogramming data entries, and clarify the requirement of finalization of the reprogrammed settings.	Modifications of requirement and clarifications.
			10.7. 2-Month Holter Study Visit	Provide option to conduct "Virtual Health Visit" in Holter study. Clarify two 6-day Holter are required for each Holter subject. Discuss the sample size requirement for the Holter study.	Providing subject with additional visit option (virtual health visit); clarifications of Holter requirement and sample size needs.
			10.8. 6-Month and 12- Month EMR Review	Provide option to conduct "Virtual Health Visit". Clarify lost to follow-up consideration due to lack of Clarity data transmission.	Providing subject with additional visit option (virtual health visit); clarifications.
			10.9. LUX-Dx ICM Not in Service, Disabled, or Explanted	Safety check window is from 30 to 60 days after the applicable events.	Clarifications of requirement.
			11.1.1. Primary Effectiveness Objective 1 11.1.2. Primary Effectiveness Objective 2	Sample size and statistical methodology for effectiveness objectives are updated to reflect the new trial design.	Update due to new trial design.
			11.1.3. Primary Safety Endpoint – Acute	Adding 2 new sections discussing the newly added safety endpoints for the study.	Addition of safety endpoints for the study.

Form/Template 92120219_Rev/Ver D
LUX-Dx PERFORM Protocol, 92557593, Rev/Ver C
Page 5 of 66

Revision Version	Protocol Date	Template number and version	Protocol Section Modified	Summary of Changes	Justification for Modification
			11.1.4. Primary Safety Endpoint - Chronic		
			11.3.1. Interim Analyses	Provide option for sample size re-estimation.	Addition of study option.
			13.1. Data Collection, Processing, and Review	Provide additional information on database lock.	Additional information.
			13.3. Technical Source Forms (TSF)	New section is added to provide additional information on TSF.	Additional information.
			16.1. Statement of Compliance	Provide additional information on clinical study agreement.	Additional information.
			16.2. Investigator Responsibilities	Provide additional information on investigator responsibilities.	Additional information.
			16.4.1. Role of Boston Scientific Representatives	Clarify the role of Boston Scientific Representatives.	Clarifications.
			18. Potential Risks and Benefits	Adding "Refer to the currently available LUX-Dx ICM User's Manual for an updated list of potential adverse events", and adding "Subject who participates in the Holter study may receive additional arrhythmia monitoring in the 14-day monitoring period by wearing the Holter monitor" as a potential benefit.	Update the reference to the currently available User's Manual mid-study and addition of potential benefit.
			19.1. Reportable Events by Study Site to Boston Scientific	Adding "Serious Adverse Device Effects" as reportable safety event for the study.	Addition of reportable event.
			19.2. Definitions and Classification 19.3. Relationship to Device(s)	Definitions and Classification of adverse events and event relationship are updated per new ISO requirement.	Update per new ISO requirement.

Form/Template 92120219_Rev/Ver D LUX-Dx PERFORM Protocol, 92557593, Rev/Ver C Page 6 of 66

Revision Version	Protocol Date	Template number and version	Protocol Section Modified	Summary of Changes	Justification for Modification
			19.4. Investigator Reporting Requirements	Adding reporting requirement for "Serious Health Threat" and updating reporting timeframe for "Serious Adverse Event", "Serious Adverse Device Effects", "Device Deficiencies", and "Adverse Event".	Updated study-specific requirement.
			21.1. Safety Monitoring Process	Clarify the safety monitoring process.	Clarifications.
			21.3. Independent Medical Reviewers – Arrhythmia Episodes 21.4. Independent Medical Reviewers – Safety Endpoints	Adding independent medical reviewers for arrhythmia episodes review and safety endpoints review.	Adding independent medical reviewers.
			22.1.1. Criteria for Premature Termination of the Study	Adding additional criteria for study termination.	Addition of study criteria.
			23. Study Registration and Results	Adding clinical study registration and clinical study report requirement.	Addition of study requirement.
			 24. Bibliography 25. Abbreviations and Definitions 26. 1. Preliminary Definitions 	Tables and references are updated from Section 24 to 26.	Updated information.
С	November 4, 2020	92120219, Rev C	Data Collection Items Version number	Updating document version number to correct a version error.	Administrative update.

2. Protocol Synopsis

LUX-Dx	Insertable Cardiac Monitor Remote Programming and Performance Study (LUX-Dx PERFORM)
Study Objective(s)	The LUX-Dx PERFORM Study will characterize, in a general patient population, the utilization of the remote programming feature of the Boston Scientific (BSC) Insertable Cardiac Monitor (ICM) device. The study will also collect data to characterize the performance of arrhythmia detection algorithms. Finally, data collected will be used to analyze and characterize the ICM system-related safety events.
Indication(s) for Use	The LUX-Dx Insertable Cardiac Monitor (ICM) is intended to monitor and record subcutaneous electrocardiogram (S-ECG). The recorded S-ECG is used for the clinical evaluation and diagnosis of cardiac arrhythmias. The LUX-Dx is indicated for use in patients that have a known heart condition and are at risk of developing an abnormal heart rhythm, or have symptoms that may suggest a cardiac arrhythmia such as dizziness, palpitations, syncope, chest pain, and/or shortness of breath. The LUX-Dx ICM has not been tested specifically for pediatric use. LATITUDE Clarity TM is intended to remotely program and interrogate a compatible Boston Scientific device via the myLUX TM patient application (patient app) or LUX-Dx Clinic Assistant application (clinic app) and transfer data to a central database. The LATITUDE Clarity Data Management System provides patient data that can be used as part of the clinical evaluation of the patient.
Test Device/System	The test devices consist of the LUX-Dx ICM, Patient and Clinic Mobile Applications, and LATITUDE Clarity Data Management System. The number of devices expected to be used are approximately the same as the number of total enrollment of the subjects in the study.
Study Design	The LUX-Dx PERFORM Study is a prospective, multi-center, single arm, post-market, observational study.
Planned Number of Subjects	Approximately 600 to 827 subjects will be enrolled in the study. This includes approximately 600 subjects participating in the extended Holter monitoring part of the study (Holter study), of which 300 subjects will come from the "Atrial fibrillation (AF) management, Post-AF ablation, or Suspected AF" indication subgroup, and 300 subjects will come from the other two indication subgroups: "Cryptogenic stroke" and "Syncope".

	Page 8 of 66				
LUX-Dx	LUX-Dx Insertable Cardiac Monitor Remote Programming and Performance Study (LUX-Dx PERFORM)				
Planned Number of Sites /Countries	This study is planned to be conducted at up to 35 sites in the United States to support the required study enrollment. It is possible that sites in Europe or Asia Pacific may join the study upon product approval in those geographies.				
	Study Objectives				
Primary Effectiveness Objective 1	Characterize the utilization of the remote programming feature				
Primary Effectiveness Objective 2	Characterize the performance of the arrhythmia detection algorithms				
Primary Safety Endpoint - Acute	ICM System-related Complication-free Rate (CFR) at 30 days post-implant				
Primary Safety Endpoint - Chronic	ICM System-related Complication-free Rate (CFR) at 12 months post-implant				
Method of Assigning Patients to Treatment	Patient who will be implanted with a BSC LUX-Dx ICM based on labelled indications and meet study-specific eligibility criteria will be considered for enrollment. To be enrolled in the study, subjects must meet all study-specific eligibility criteria and sign the study-specific Informed Consent Form (ICF).				
Follow-up Schedule	All subjects must complete the enrollment visit before receiving implantation of the LUX-Dx ICM. Following consent into the study, relevant data including reportable adverse events and ICM device data from the LATITUDE Clarity will be collected during the subject's study participation period. Specifically, participating sites will be requested to review each enrolled subject's electronic medical record (EMR) and communicate with the subject by conducting telephone call/virtual health visit or in-office visit if scheduled per standard of care to the subject at two primary time points (6 months and 12 months post-implant) for relevant adverse events. Each subject's study participation period will be approximately one year or until BSC notifies all sites that data collection is complete.				

LUX-Dx Insertable Cardiac Monitor Remote Programming and Performance Study (LUX-Dx PERFORM)

Additionally, extended Holter monitoring (defined as a monitoring period of 14 days) will be conducted with a subset of subjects at the 2-month in-office visit or remotely by telephone/virtual health visit. To determine which subjects are required to join the Holter study, the following study cohorts are specified:

- The first 227 subjects enrolled in the study belong to the "Safety Cohort". The number of subjects is required to fulfill the sample size requirement of the primary safety endpoint. The "Safety Cohort" subjects are not required to participate in the Holter study.
- Once the "Safety Cohort" enrollment is completed, all subsequent subjects are required to participate in the Holter study.
- All subjects who participate in the Holter study belong to the "Holter Cohort", which is to fulfill the sample size requirement of the primary effectiveness objective 2.

Study Duration	The study is expected to last approximately 3.5 years from the first enrollment to study closure.	
Participant Duration	The study duration for each enrolled subject is expected to be approximately 12 months.	
Inclusion Criteria	• Patient is indicated to be implanted with the LUX-Dx ICM for one of the following reasons (grouped in three "Reason for Monitoring" subgroups):	

LUX-Dx	Insertable Cardiac Monitor Remote Programming and Performance Study (LUX-Dx PERFORM)
Exclusion	 Cryptogenic stroke Syncope AF management, Post-AF ablation, or Suspected AF Patient is willing to enroll and be monitored in LATITUDE Clarity. Patient is willing and able to be followed remotely via the ICM patient mobile app. Patient is willing and capable of providing informed consent (which is not to include the use of a legally authorized representative (LAR) for documentation of informed consent) and agrees to participate in all protocol required activities. Patient is age 18 years or above, or of legal age to give informed consent specific to state and national law. The following inclusion criterion is applicable for patients participating in the Holter study: Patient can tolerate the adhesive used in the Holter monitoring for an extended period of time.
Criteria	 Patient is indicated for implaintation of, or is currently implained with an active implantable cardiac device (e.g., LVAD, ICD, CRT-D, PPM*). Patient cannot tolerate a subcutaneous, chronically-inserted device due to medical condition. Patient has a documented life expectancy of less than 12 months (per investigator's discretion). Patient is known to be pregnant at the time of study enrollment (method of assessment upon investigator's discretion). Patient is currently enrolled in another clinical study including observational studies/registries, unless prior written approval from BSC is obtained. Mandatory governmental registries are accepted for co-enrollment without approval by BSC. The following exclusion criteria are applicable for patients participating in the Holter study: Patient has known allergies to the adhesive materials or hydrogel used in the extended Holter monitoring. Patient has broken, damaged, or irritated skin over the chest area where the extended Holter monitor will be attached.

LUX-Dx	Insertable Cardiac Monitor Remote Programming and Performance Study (LUX-Dx PERFORM)
	*LVAD: Left Ventricular Assist Device; ICD: Implantable Cardioverter Defibrillator; CRT-D: Cardiac Resynchronization Therapy-Defibrillator; PPM: Permanent Pacemaker
Statistical Meth	ods
Primary Statistical Hypothesis	 There are no primary effectiveness hypotheses but rather primary effectiveness objectives which involve characterizing and summarizing data. The primary safety endpoint - acute hypotheses are: H₀: ICM system-related complication-free rate at 30 days post-implant ≤ 94%
	 H_A: ICM system-related complication-free rate at 30 days post-implant > 94% The primary safety endpoint - chronic hypotheses are:
	 H₀: ICM system-related complication-free rate at 12 months post-implant ≤ 93% H_A: ICM system-related complication-free rate at 12 months post-implant > 93%
Statistical Test Method	Primary Effectiveness Objective 1: Remote Programming Primary Effectiveness Objective 2: ICM algorithm performance Primary Effectiveness Objective 2: ICM algorithm performance Primary Safety Endpoint - Acute: ICM system-related complication-free rate • Kaplan-Meier rate with a one-sided pointwise log-log confidence limit Primary Safety Endpoint - Chronic: ICM system-related
	Primary Safety Endpoint - Chronic: ICM system-related complication-free rate

LUX-Dx	Insertable Cardiac Monitor Remote Programming and Performance Study (LUX-Dx PERFORM)
	Kaplan-Meier rate with a one-sided pointwise log-log confidence limit
Sample Size Parameters	Approximately 600 to 827 subjects will be enrolled to fulfill the objectives and safety endpoints. Approximately 600 subjects are desired for sufficient data in the Holter study and 227 subjects are needed for the safety endpoints. A total of 227 enrollments are required for the safety endpoint but the first 227 subjects do not enroll in the Holter study then a maximum sample size would be 827. The overall sample size is based on the Holter study and the primary safety endpoint – acute.

92557593 C.3 Page 13 of 66

3. Table of Contents

1.	TITL	LE PAGE	1
2.	Pro	TOCOL SYNOPSIS	7
3.	TAB	LE OF CONTENTS	14
	3.1.	Table of Figures	
	3.2.	Table of Tables	
4.	Intr	RODUCTION	19
	4.1.	Background	19
	4.2.	Study Rationale	19
5.	LUX	X-Dx ICM Device/System Description	19
	5.1.	LUX-Dx ICM	20
	5.2.	Mobile Applications	20
	5.3.	LATITUDE Clarity Data Management System	21
	5.4.	Additional Required Medical Equipment and the Associated	Procedures22
6.	STUI	DY OBJECTIVES AND ENDPOINTS	22
7.	STUI	dy Design	23
	7.1.	Scale and Duration	23
	7.2.	Treatment Assignment	24
	7.3.	Justification for the Study Design	24
8.	Subj	JECT SELECTION	25
	8.1.	Study Population and Eligibility	25
	8.2.	Inclusion Criteria	25
	8.3.	Exclusion Criteria	26
9.	Subj	JECT ACCOUNTABILITY	27
	9.1.	Point of Enrollment	27
	9.2.	Enrollment Control	27

4.1. Background

Cardiac arrhythmias, especially atrial fibrillation (AF), affect millions of people worldwide. Standard of care methodologies to detect and diagnose these arrhythmias include electrocardiogram (ECG), ambulatory rhythm monitoring (e.g. Holter monitor), mobile cardiac outpatient telemetry (MCOT), and cardiac implantable electronic devices (CIED) with arrhythmia detection and therapeutic capabilities such as pacemakers and defibrillators.^{1,2} Non-invasive diagnostic techniques have drawbacks including patient compliance and limited duration of monitoring, while pacemakers and defibrillators are restricted to only those patients meeting indications for therapy (bradycardia and/or tachycardia) once the diagnosis has already been established in most cases.³⁻⁷

To fill this gap and to aid clinicians in determining the cause of symptoms such as unexplained syncope and palpitations, insertable cardiac monitors (ICMs) that allow for long-term cardiac rhythm monitoring and require a simple subcutaneous implant procedure with a low complication rate have been developed.⁸⁻¹¹ This approach has shown promising results in patients who are at increased risk of cardiac arrhythmias.¹²⁻¹⁶

Boston Scientific (BSC) has developed an ICM system, LUX-DxTM, which is indicated for use in patients that have a known heart condition, are at risk of developing an abnormal heart rhythm, or have symptoms that may suggest a cardiac arrhythmia (e.g. dizziness, palpitations, syncope, chest pain, and/or shortness of breath). The LUX-Dx ICM uses a data management system, LATITUDE ClarityTM, which allows clinicians to remotely monitor and program the ICM. In order to transfer the ICM device data to LATITUDE Clarity, the system utilizes the myLUXTM mobile patient app. This allows clinicians to access the device data for analysis to support their evaluation of the clinical status and to adjust the diagnostic programmable features as needed.

4.2. Study Rationale

Real-world clinical data for patients implanted due to cryptogenic stroke, suspected AF, syncope, AF management, or post-AF ablation are necessary to understand the usage of remote programming, the performance of arrhythmia detection algorithms of the LUX-Dx ICM, and the safety of the ICM system. This trial's patient population is representative of the majority of the intended recipients of the LUX-Dx ICM. The data collection in the LUX-Dx \underline{Dx}^{TM} Insertable Cardiac Monitor Remote Programming and Performance Study (LUX-Dx PERFORM) may also be used by BSC for future product enhancements and support future regulatory submissions.

5. LUX-Dx ICM Device/System Description

Refer to Table 5-1 for a summary of the LUX-Dx ICM system components used in the study.

5.1. *LUX-Dx ICM*

The LUX-Dx ICM is a small, leadless electronic device implanted under the skin in the left anterior chest wall. Its primary functions are to monitor, record, and store data related to cardiac arrhythmias. Two electrodes on the body of the device are used to monitor and record the patient's subcutaneous ECG (S-ECG) data when specific arrhythmias (according to the device-programmed settings) are detected, which include pause, bradycardia, tachycardia, AF, and atrial tachyarrhythmias (AT). In addition, the device will record S-ECG data when the patient triggers the device to record via the myLUX patient app. The ICM's memory can store up to 60 minutes of S-ECG recordings. Initial default arrhythmia detection parameters are provided by LATITUDE Clarity according to the Reason for Monitoring. However, these can be configured and adjusted by the clinician according to the subject's clinical indication.

5.2. Mobile Applications

There are two mobile applications used to interrogate the LUX-Dx ICM and transmit data from the device to the LATITUDETM server: a patient-specific app called **myLUX**, and a clinic-specific app called **LUX-Dx Clinic Assistant**. The patient app also allows patients to record and send S-ECGs of symptomatic events to the LATITUDE server. Both apps communicate with the device using Bluetooth Low Energy (BLE) technology, and with the LATITUDE server using a Wi-Fi or cellular connection. Refer to Figure 5-1 for a diagram of the LUX-Dx ICM System.

Form/Template 92120219_Rev/Ver D LUX-Dx PERFORM Protocol, 92557593, Rev/Ver C Page 21 of 66

5.3. LATITUDE Clarity Data Management System

LATITUDE Clarity Data Management System consists of a central LATITUDE server and website. LATITUDE Clarity is the website's diagnostics environment that is used to program the LUX-Dx ICM and to review and evaluate clinical data. All remotely transmitted data is sent to the LATITUDE server and is available on the LATITUDE Clarity website to authorized health care providers. Data stored on LATITUDE Clarity during subject's study participation will be used to support analysis of the study objectives.

System Component	Description	Model Number
ICM Device	LUX-Dx Insertable Cardiac Monitor (ICM)	M301
	myLUX software (patient app)	2925
Mobile Applications*	LUX-Dx Clinic Assistant software (clinic app)	2935
Server and Website	LATITUDE Clarity Data Management System	7260
Items Included in Package Additional Tools	The following sterile items are included in the package: • Insertable Cardiac Monitor device preloaded in the insertion tool • Incision tool • Sterile pouch	(part of M301)
Additional Tools used during implant, but not packaged with it	 Mobile device** with patient app or clinic app pre-installed Magnet Mobile device power adapter with USB cable (as needed) 	6259 myLUX 6256 LUX-Dx Clinic Assistant 6386 magnet

Table 5-1: BSC LUX-Dx ICM Device and Associated Components

*Future mobile or firmware applications may be used when they receive product clearance from regulatory agenc(ies)

**Including future mobile devices when they are available for use in the study

5.4. Additional Required Medical Equipment and the Associated Procedures

A commercially approved Holter monitor and its accessories will be provided for the study sites to conduct the 14-day, extended Holter monitoring part of the study (Holter study). The equipment and monitoring service will be provided by an independent Core lab. Refer to Section 10.7 for a description of the Holter study methodology.

6. Study Objectives and Endpoints

The first primary objective of the LUX-Dx PERFORM Study is to characterize the utilization of the remote programming feature of the ICM in a real-world setting. Also, the study will characterize the performance of the arrhythmia detection algorithms based on episodes detected and recorded by the LUX-Dx ICM as well as compared to an extended Holter monitor. Finally, data collected will be used to analyze and characterize ICM system-related safety events. There are two safety endpoint hypotheses in this study. A safety performance goal is established for the ICM system-related complication-free rate at 30 days and at 12 months post-ICM implant, respectively.

7. Study Design

The LUX-Dx PERFORM Study is a multicenter, prospective, single-arm, post-market, observational study.

7.1. Scale and Duration

The LUX-Dx PERFORM Study is planned to be conducted at approximately 25 to 35 sites in the US and will enroll approximately 600 to 827 subjects. The final enrollment number is driven by the number of subjects participating in the Holter study. It is possible that study sites from Europe or Asia Pacific may participate upon product approval in those geographies. The number of sites may go up to 35 sites if it is required to sufficiently support the study enrollment completion. Sites may continue to enroll subjects until notified by BSC of enrollment completion. Additional provisions for each site's enrollment are specified in Section 11.2.3.

The first 227 subjects belong to the "Safety Cohort", and must be enrolled to satisfy the sample size required for the safety endpoint analysis. See Section 11.1.5. for detailed discussion on sample size requirements.

The ICM implant procedure must be performed within 30 days following the subject consent. Relevant study data including implant procedure-related data, reportable adverse events, and ICM device data from the LATITUDE Clarity will be collected during the subject's study participation period. Specifically, participating sites will review each enrolled subject's electronic medical record (EMR) and communicate with the subject via telephone calls/virtual health visit or in-office visit that might be part of the standard of care at two primary time points (6 months and 12 months after implant) for relevant adverse events. For the purpose of this study, these follow-up visits do not require subjects' physical presence at the study site. Each subject's study participation period will be approximately one year from the point of device implant or until BSC notifies all sites that data collection is complete.

Defined as the "Holter Cohort", a subset of approximately 600 subjects will wear an extended Holter monitor for a monitoring period of approximately 14 days. This will be performed at the 2-month in-office visit or remotely by telephone call/virtual health visit. The purpose of the Holter cohort is for calculating diagnostic performance of the ICM.

Refer to Figure 7-1 for a diagram of the study design, subject cohort, and flowchart.

Figure 7-1: Study Design, Subject Cohort, and Flow Diagram

Enrollment is expected to be completed in approximately 30 months; therefore, the total study duration is estimated to be approximately 3-4 years. The total study duration for each implanted subject is approximately 12 months.

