7.3. Justification for the Study Design

The objective of the LUX-Dx PERFORM Study is to collect data in a clinical setting reflecting real-world usage of the LUX-Dx ICM. Therefore, a prospectively enrolled, observational, post-market study design was determined to be appropriate. Subject enrollment requirements are supported by the following:

- A sample size of 227 subjects will be required to power the first primary safety endpoint analysis (acute endpoint), and 226 subjects will be required to power the second primary safety endpoint (chronic endpoint).
- The Holter study group is expected to enroll approximately 600 subjects, including approximately 300 subjects from the "AF management, Post-AF ablation, or Suspected AF" subgroup, and approximately 300 subjects from the other 2 subgroups ("Syncope" and "Cryptogenic stroke"). The distribution of the device indications is desired to generate at least 100 subjects with a detected AF episode during the Holter

	Form/Template 92120219_Rev/Ver D			
Confidential	LUX-Dx PERFORM Protocol, 92557593, Rev/Ver C			
	Page 25 of 66			
monitoring period. Refer to Section 11.1.2.2 for rationales of the sample size				

requirement in the Holter study.

Refer to Section 11 for details of overall study sample size discussion.

8. Subject Selection

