11.1.3.2. Statistical Methods

The ICM system-related complication-free rate at 30 days post-implant will be calculated using Kaplan-Meier methodology. The 97.5% one-side lower pointwise confidence limit of

	Form/Template 92120219_Rev/Ver D
Confidential	LUX-Dx PERFORM Protocol, 92557593, Rev/Ver C
	Page 38 of 66

the ICM system-related complication-free rate will be calculated via log-log methodology and compared to the performance target of 94%. If the lower confidence limit exceeds 94% then the null hypothesis will be rejected.

The adjudication of the ICM system-related adverse events and complications will be conducted by independent physician reviewer(s).

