11.1.4.2. Statistical Methods

The ICM system-related complication-free rate at 12 months post-implant will be calculated using Kaplan-Meier methodology. The 97.5% one-side lower pointwise confidence limit of the ICM system-related complication-free rate will be calculated via log-log methodology and compared to the performance target of 93%. If the lower confidence limit exceeds 93% then the null hypothesis will be rejected.

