11.2. General Statistical Methods

11.2.1. Analysis Sets

Data from Implant and Attempt subjects will be used for each objective and endpoint as appropriate. Further details will be outlined in the Statistical Analysis Plan.

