11.2.2. Control of Systematic Error/Bias

The number of subjects each center can enroll will be capped and poolability of data will be tested across centers to assess heterogeneity. Additionally, the first 227 enrollments for the safety cohort will not be required to enroll in Holter study to avoid subject selection bias.

Form/Template 92120219_Rev/Ver D Confidential LUX-Dx PERFORM Protocol, 92557593, Rev/Ver C Page 40 of 66

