11.2.3. Number of Subjects per Investigative Site

To avoid any study site effect and bias, no single site will enroll more than 90 subjects of the total enrollments in the study and 34 subjects for the safety endpoint, without prior approval from BSC.

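### Do the safety tests waste data, or stay open to a late choice, because the protocol does not say whether they use the first 227 enrollees or everyone?

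*Combined protocol and SAP*

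**What the plan says.** The protocol tests two hypotheses, both on safety. The Kaplan-Meier complication-free rate at 30 days is "compared to the performance target of 94" percent (Section 11.1.3.2). The rate at 12 months is "compared to the performance target of 93" percent (Section 11.1.4.2). The rule is the same for both: "The 97.5% one-side lower pointwise confidence limit of the ICM system-related complication-free rate will be calculated via log-log methodology".

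Some passages point to the first 227 enrollees as the safety population:
- Section 7.3: "A sample size of 227 subjects will be required to power the first primary safety endpoint analysis".
- Section 7.1 calls the first 227 the Safety Cohort and says they "must be enrolled to satisfy the sample size required for the safety endpoint analysis".
- Section 11.2.3 has a separate site cap: "no single site will enroll more than 90 subjects of the total enrollments in the study and 34 subjects for the safety endpoint".
- Section 11.2.2 gives a reason for the cohort: "the first 227 enrollments for the safety cohort will not be required to enroll in Holter study to avoid subject selection bias".

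Other passages point to everyone:
- Section 11.2.1: "Data from Implant and Attempt subjects will be used for each objective and endpoint as appropriate", with further detail left to the SAP.
- Section 9.5 includes implanted subjects in every analysis that applies to them.
- Section 10.8 gives each implanted subject the same reviews at 6 and 12 months.

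Section 11.3.5 governs changes. Those made before an analysis need an amended SAP approved before it is run. Later ones must be reported, with a reason, in the study report.

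**The concern.** Two readings of the safety analysis set are open, and they differ nearly threefold to fourfold in size. If only the first 227 are analysed, most of the adverse-event data, collected in the same way, stays out of both tests. The standard error is then 1.63 to 1.91 times what it could be.

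If the set is not fixed early, the result may depend on which set is taken. At an assumed true 30-day rate of 97%, the first 227 fail while all subjects pass in 46% of studies (600 in total) to 51% (827 in total).

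The setting adds to the worry. The study has one arm, sponsor staff review safety data as they arrive (Section 21.1), informal interim analyses are allowed (Section 11.3.1), and the sponsor may stop or extend Holter enrollment (Section 10.7), so the size of the full set is itself settled during the study. At stake would be an imprecise estimate, or a pass that owes something to the choice of set.

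**Working it through.** **Inputs.** Goals 94% and 93%, one-sided 2.5%, log-log lower limit (Sections 11.1.3.2 and 11.1.4.2). Safety sample sizes 227 and 226 (Section 7.3). Total 600 to 827 (Section 11.1.5). True rates and complete follow-up are assumptions.

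**The plan's own figure.** The expected rate, power and attrition behind 227 are not in the available text (Section 11.1.3.3 is listed in the contents, but its text is not there), so 227 can be neither reproduced nor refuted. It is plausible. With an assumed true rate of 98% and 80% power, the normal approximation gives

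n = [(1.960 × √(0.94 × 0.06) + 0.842 × √(0.98 × 0.02)) / 0.04]² = 213,

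and 213 / 0.95 = 225 with an assumed 5% attrition. Exact power with 227 is 82.8%. For the chronic endpoint, 226 subjects give 76% power at an assumed 97% and 88% at 97.5%.

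**Share and precision.** Outside the first 227: 1 − 227/600 = 62.2%, and 1 − 227/827 = 72.6%. Standard-error ratios: √(600/227) = 1.63 and √(827/227) = 1.91.

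**Passing rule.** With x events in n subjects, S = 1 − x/n, se = √((1 − S)/(nS)) / |ln S|, and the lower limit is S^exp(1.96 × se). For 6 of 227: S = 0.9736, se = 0.408, limit = 0.9736^2.226 = 94.2%, a pass. For 7 of 227 the limit is 93.6%, a fail. The largest passing count and the exact binomial probability of passing are:

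| Goal | n | Most events that pass | False pass at the goal | Power at 96% | Power at 97% | Power at 98% |
|---|---|---|---|---|---|---|
| 94% | 227 | 6 | 1.6% | 19% | 48% | 83% |
| 94% | 600 | 24 | 1.9% | 55% | 93.5% | 99.9% |
| 94% | 827 | 36 | 2.3% | 73% | 98.8% | >99.9% |
| 93% | 227 | 8 | 2.0% | 44% | 76% | 96% |
| 93% | 600 | 29 | 1.9% | 87% | 99.5% | >99.9% |
| 93% | 827 | 43 | 2.1% | 96% | >99.9% | >99.9% |

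Every false-pass rate is below 2.5%, so the test is valid on either set.

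**Free choice of set.** The first 227 are nested in the total N. With a and b the largest passing counts in the 227 and in N, X₁ the events in the 227 and X₂ those in the rest, the chance that at least one set passes is P(X₁ ≤ a) + Σ over k > a of P(X₁ = k) × P(X₂ ≤ b − k). At the goal this gives 3.1% (N = 600) and 3.6% (N = 827) for acute, and 3.4% and 3.8% for chronic. A simulation of 2,000,000 runs agrees. This is the worst case, in which the sponsor sees both results and reports only the better one.

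**The text side by side.** The Section 7.1 sentence states how many must be enrolled. Sections 7.3, 9.2.1 and 11.1.5 likewise say what is required or needed. None excludes later subjects. The site cap of 34 is 34/227 = 15.0% of the cohort, just as 90/600 = 15.0% of the study, which suggests that the cohort was meant as the test set. Sections 9.5 and 11.2.1 permit the wider set. The text therefore leaves the set to be named later; it does not state a rule that is wrong.

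**The case for a change.** The strongest case for a change runs as follows. These are the only two hypothesis tests in the study, the available text fixes no set for them, and Section 11.3.5 controls changes to a plan without defining the set. Naming it would cost a sentence and one extra run. At an assumed acute rate of 98% the two sets would still disagree, with the 227 failing and all subjects passing, in 17% of studies.

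Part of this stands. The available text does not choose, and a reader would like to see the choice. It is also true that Section 9.1 counts enrollment at consent, so subjects who never reach the implant procedure (Intent, Section 9.5) count toward the 227 but fall outside the Implant and Attempt data. Whether 227 allows for this cannot be checked.

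The rest does not carry a change. The separate SAP to which Section 11.2.1 defers is not part of the text reviewed here and may already name the set. The natural remedy, testing in the first 227 and showing all subjects as support, leaves the tests and their power as they are and only adds a display. Moving the tests to all subjects would give up the protection against Holter-related selection that Section 11.2.2 offers as its reason, because later enrollees must accept the Holter study and meet its skin and adhesive criteria.

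Nor can it be said that the first 227 carry a learning effect. They are the first study-wide, not the first at each site, and the documents give no learning data for this marketed device.

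**Conclusion.** No change to the plan is needed. This is a gap that the SAP author fills in the ordinary course: the Safety Cohort wording and the 34-subject cap point to the first 227 for the tests, and nothing stops an all-subject estimate from being shown beside them. Lost precision arises on one reading only, and on that reading it is the price of a cohort not selected for Holter participation. Either set keeps the false-pass rate at 1.6% to 2.3%, and unrestricted choice between them would bring it to 3.1% to 3.8% against 2.5%.

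The power gap between the sets is real, but it depends on true rates that the available text does not give. At an assumed 98% (acute) and 97% (chronic), 227 subjects have 83% and 76% power, so the number is not shown to be too small for its purpose. All these figures assume complete follow-up and the same true rate in early and later enrollees.
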